8.2 Secondary Efficacy Analyses

Logistic analyses will be utilized to determine if there is treatment effect based on the best ear outcome. As in the total ear analysis, change in the best ear will be categorized into binary outcomes – namely: improved + no change versus worse; improved + no change (normal to normal) versus worse + no change (abnormal to

abnormal); and improved versus other between baseline and Study Month 6. In addition to the primary outcome, we will analyze the binary outcome for change in the total ears categorized as: improved+ no change (normal to normal) versus worse and improved vs other.

For other secondary and tertiary outcomes, Fisher's exact test will be used to compare binary outcomes (such as detection of viruria or subject with at least one AE or SAE), and Wilcoxon Rank test will be used to compare continuous outcomes (such as quantitative log reduction) between the two treatment groups 6 weeks and 6 months after initial treatment.

Logistic model utilizing generalized estimating equations will also be used to determine the association between change in hearing and change in viral load. Change in viral load over time will be measured by the area under the curve computed using the trapezoidal rule. Spearman rank correlation will be utilized to examine the association between viral load and PK parameters. Poisson regression model will be used to compare the number of AEs/SAEs experienced by subjects between the two groups.

As in the primary outcomes, missing change in hearing outcomes will be replaced by worsened outcomes as sensitivity analyses for all secondary hearing outcomes.

The summary statistics will be produced in accordance with section 7.

9 Safety Analyses

Analyses of safety data will be based on data from all subjects receiving at least one dose of study drug. As per protocol, safety data will be collected only through Study Day 70, i.e., four weeks after the last study dose.

Incidence of serious and non-serious adverse events will be summarized by body system and system organ class using Medical Dictionary of Regulatory Activities (MedDRA) codes, the United States Division of AIDS (DAIDS) toxicity grade, and relation to drug. Frequencies (numbers and percentages) of subjects with one or more adverse events will be summarized by treatment group. Incidence of neutropenia and the incidence of adverse events leading to discontinuation of therapy will be assessed. Fisher's exact test will be used to compare proportions and Wilcoxon rank sum test will be used to compare continuous safety parameters

between two groups. Poisson regression model will be used to compare the number of AEs experienced by subjects between two groups.

Raw listings of all AEs and SAEs will be provided sorted by treatment group, subject ID and onset date.

When calculating the incidence of AEs by toxicity grade for a given body system, the most severe AE will be counted for subjects with multiple AEs.

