#### **3.2.2. Secondary Outcome Measures**

- Change in best ear hearing assessments [improved + no change (normal to normal) versus other; improved versus other; worse + no change (abnormal to abnormal) versus other; and worse versus other] between Baseline and Study Month 6
- Change in total ear hearing assessments (improved versus other; worse + no change (abnormal to abnormal) versus other; and worse versus other) between Baseline and Study Month 6
- Detection of viruria by PCR six weeks and six months after trial entry

- The quantitative log reduction in viruria detected after 6 weeks of therapy
- Detection of viremia by PCR six weeks and six months after trial entry
- The quantitative log reduction in viremia detected after 6 weeks of therapy
- Detection of CMV in saliva by PCR six weeks and six months after trial entry
- The quantitative log reduction in CMV viral load in saliva detected after 6 weeks of therapy
- Correlation of change in viral load with change in total ear and best ear hearing at 6 months
- Incidence of unanticipated medically attended visits occurring from Study Day 1 through two weeks following the last dose of study drug
- Incidence of adverse events which lead to permanent discontinuation of valganciclovir therapy or have an unresolved outcome

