### 5.2. Subject Inclusion Criteria

- Signed informed consent from parent(s) or legal guardian(s)
- Sensorineural hearing loss ( $\geq 21$ dB in one or both ears, documented within 12 weeks prior to study entry)
- Children from 1 month through 3 years of age (up to the 4th birthday)

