### **11.2. Sample Size Considerations**

Subjects will be randomized 1:1 to valganciclovir oral solution or valganciclovir placebo. A **sample size of 54 (27 in each arm)** has 90% power to detect a worsening of hearing from 40% to 8.0% in the treatment group based on analyzing two correlated binary outcomes with correlation coefficient of 0.55 at 2.5% level of significance (using PASS 2008 program). Randomization will be stratified by age at randomization (1 through 11 months, 12 through 23 months, 24 through 35 months, and  $\geq 36$  months) and by CMV involvement (symptomatic and asymptomatic at birth) as a marker of disease severity.

Efficacy and safety analysis will be based on intent-to-treat population (ITT), defined as any child who receives at least one dose of study medication and who has complete hearing assessment data at baseline and Month 6. Children who completed the full six weeks of study medication and have hearing assessment data at baseline and Month 6 will be included in a per protocol (PP) analysis of efficacy, which will be performed as a sensitivity analysis. Since the primary endpoint requires comparison of baseline and 6 month audiology assessments, dropouts and subjects with audiology assessments that are inadequate for study comparison will be replaced.

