### **11.4.2. Secondary and Tertiary Outcomes**

Logistic analyses will be utilized to determine if there is treatment effect based on the best ear outcome. As in the total ear analysis, change in the best ear will be categorized into binary outcomes – namely: 1) improved + no change versus others, which examines positive hearing outcomes defined as improved hearing or protection from hearing impairment in subjects who started with normal hearing at baseline; 2) worsened versus others, which examines deterioration or worsening of hearing; 3) improved versus others; and 4) worse + no change versus others. Similar analyses will be performed for total ears (worsened versus others, improved versus others, and worse + no change versus others).

For other secondary and tertiary outcomes, Fisher's exact test will be used to compare binary outcomes (such as detection of viremia or subject with at least one AE or SAE), and Wilcoxon Rank test will be used to compare continuous outcomes (such as quantitative log reduction) between the two treatment groups 6 weeks and 6 months after initial treatment.

Logistic model utilizing generalized estimating equations will also be used to determine the association between change in hearing and change in viral load. Change in viral load over time will be measured by the area under the curve computed using the trapezoidal rule. Spearman rank correlation will be utilized to examine the association between viral load and PK parameters. Poisson regression model will be used to compare the number of AEs/SAEs experienced by subjects between the two groups.

As in the primary outcomes, missing change in hearing outcomes will be replaced by worsened outcome as sensitivity analyses for all secondary hearing outcomes..

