3.3 Derived variables

The primary efficacy assessment will be change in total ear hearing assessment between baseline and 6 months post enrollment. Categories used for hearing assessment of each ear for each time point will be normal hearing, mild hearing loss, moderate hearing loss, and severe hearing loss. Baseline and 6 month hearing categories will be compared and the change in each ear will be categorized into binary outcomes: Improved or no change versus Other (i.e., worsened) Note that the total ear assessment at each time point will be provided by the Independent Audiologist and entered in the database following the rules below and the information provided by the audiology reports.

In the model-based analyses, the “no change” category will be broken down into “Protected: normal to normal” as one category and “No Change: same degree of hearing loss at Baseline and Study Month 6” as another category. The rationale behind this is that if one is interested in the improvement of hearing loss, a subject that has normal hearing at baseline cannot improve further. Hence from an efficacy analysis point of view, the “Protected: normal to normal” can be viewed as protective effect of the drug from hearing deterioration. This analysis approach will be similar to the analysis of the previous CASG study that established the efficacy of 6 weeks of IV GCV in symptomatic congenital CMV disease with CNS involvement.

Analysis of actual viral load will be done using log base 10 transformation. Undetectable viral load value will be replaced by a value of 10. A summary measure of the viral load over time will be calculated two ways. The first approach considers all time points available by calculating the average area under the curve (AUC) (trapezoidal rule) applied to the log base 10 viral load. Average is based on the maximum period of time with viral load data for a given subject. To illustrate, if the calculated AUC for log₁₀ VL for a given subject is 200 from baseline to Day 70, then average AUC is $200/70=2.86$. Taking average AUC will enable us to use and compare data from subjects who did not have viral load values at the later time due to dropping out early, for example, with subjects with complete viral load data. The second approach is to take using difference between Month 6 and baseline log₁₀ VL. The last visit with available VL will be used for those without Month 6 VL. Section 11 contains more details on Viral Load analyses.

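### SAP 8.2 leaves ears that stay abnormal out of one total-ear secondary contrast, so ears are selected by their Month 6 result and a protocol endpoint has no matching analysis

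*SAP*

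**What the plan says.** The total-ear secondary endpoint is set in Protocol 3.2.2: "Change in total ear hearing assessments (improved versus other; worse + no change (abnormal to abnormal) versus other; and worse versus other". SAP 3.2 repeats it as its second secondary endpoint. Protocol 11.4.2 carries it into the analysis: "Similar analyses will be performed for total ears (worsened versus others, improved versus others, and worse + no change versus others". Each of these contrasts sets one group of ears against all the rest, so every evaluable ear is classified.

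SAP 8.2 lists two total-ear contrasts beyond the primary: "improved+ no change (normal to normal) versus worse and improved vs other". Just before this, the same section gives the best-ear version with a full comparator: "improved + no change (normal to normal) versus worse + no change (abnormal to" abnormal).

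SAP 3.3 splits unchanged ears for the model-based analyses. Ears normal at both visits are called protected. The others form their own category, "No Change: same degree of hearing loss at Baseline and Study Month 6".

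**The concern.** There are four possible outcomes for an ear: improved, protected (normal at both visits), stable-abnormal, and worse. The first total-ear contrast in SAP 8.2 uses three of them. A programmer following it literally would set stable-abnormal ears to missing, because no text assigns them to the worsened group.

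Whether an ear enters the model would then depend on its Month 6 result. That is selection after randomisation, and it can differ between arms. It also means that a child can contribute two, one or no ears to the GEE model.

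The omitted class is not marginal. Every child must have hearing loss "in one or both ears, documented within 12 weeks prior to study entry", so at least half of the ears start abnormal if the eligibility and baseline gradings agree. The trial's aim is to stabilise hearing, and an ear with existing loss that is stabilised falls in the omitted class. A real reduction in worsening could therefore be reported as a gain in improvement or protection. In addition, the protocol endpoint that groups worsened with stable-abnormal ears has no matching total-ear analysis in SAP 8.2.

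**Working it through.** **The plan's own figure.** The documents give no number for this contrast. The only related figure is the power for the primary endpoint (Protocol 11.2, SAP 5): 90% with 27 children per arm, worsening of 40% versus 8%, correlation 0.55 and a 2.5% level. Two ears per child give 2 × 27 / (1 + 0.55) = 34.84 effective ears per arm. A two-proportion test with pooled variance then has 89.6% power at 2.5% one-sided, which agrees with the plan. At 2.5% two-sided it would be 83.0%; the documents do not state the sidedness. This shows that 40% and 8% work as per-ear rates on up to 54 ears per arm, and they are used that way below.

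**Which ears each contrast uses.**

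| Ear outcome | Protocol 3.2.2, SAP 3.2 | SAP 8.2, best ear | SAP 8.2, total ear |
|---|---|---|---|
| Improved | favourable | favourable | favourable |
| Normal at both visits | favourable | favourable | favourable |
| Stable-abnormal | unfavourable | unfavourable | in neither group |
| Worse | unfavourable | unfavourable | unfavourable |

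**Illustration.** Worsening is 40% (placebo) and 8% (active), from the plan. Assume that a share s of ears is improved or protected in both arms, so every prevented worsening becomes a stable-abnormal ear. Neither s nor its equality across arms is in the documents.

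- Protocol contrast: s versus s, odds ratio 1.0.
- SAP 8.2 contrast: s/(s + 0.40) versus s/(s + 0.08). The odds ratio is (s/0.08)/(s/0.40) = 5.0 for any s up to 0.60.
- With s = 0.20: 0.20/0.60 = 33% versus 0.20/0.28 = 71%. The ears discarded are 1 − 0.60 = 40% (placebo) and 1 − 0.28 = 72% (active).
- Over a range (protected 10% to 25%, improved 5% to 15%, so s from 0.15 to 0.40), the SAP contrast keeps 29.7 to 43.2 of 54 placebo ears and 12.4 to 25.9 of 54 active ears.

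**A less extreme case.** Assume instead that 20% of ears are normal at baseline, 10% of all ears improve in both arms, and worsening is 40% versus 8% whatever the baseline state.

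- Protected: 0.20 × 0.60 = 12% versus 0.20 × 0.92 = 18.4%.
- Protocol contrast: 22% versus 28.4%, odds ratio (0.284/0.716)/(0.22/0.78) = 1.4.
- SAP contrast: 0.22/0.62 = 35% versus 0.284/0.364 = 78%, odds ratio (0.284/0.08)/(0.22/0.40) = 6.5.

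**The precedent that the SAP names.** SAP 3.3 says the approach follows the earlier study of intravenous ganciclovir. Protocol 2.1.2.1 gives its best-ear results. Improved or normal at both times: 21/25 versus 10/17. Worse: 0/25 versus 7/17. Hence 25 − 21 − 0 = 4 treated and 17 − 10 − 7 = 0 untreated children were in neither group, and they stayed in the denominators.

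- All children: 84% versus 59%, reported adjusted P = 0.06 (unadjusted Fisher P = 0.086).
- Without those four: 21/21 = 100% versus 10/17 = 59%, Fisher P = 0.0015.

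All four children lost come from the treated arm.

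**The case against.** The strongest reply is that this is an omitted phrase and not a decision to exclude ears. Where the SAP intends exclusions it says so, for ineligible subjects, post-implant hearing data and missing audiology. SAP 3.2 states the endpoint correctly, the best-ear text in SAP 8.2 has the full comparator, and the named precedent kept all evaluable children. That reading is probably right about intent. However, SAP 8.2 is the operative analysis text, and calling the outcome binary does not say where stable-abnormal ears go.

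A second reply is that the first illustration is one extreme. It sends all of the benefit into the stable-abnormal class, whereas normal ears that are protected would raise the favourable class. Protocol 2.1 reports unilateral loss in 33% to 52% of affected children, so normal ears at baseline are to be expected. This stands as a limit on the exact size. The second case above allows for it, and the gap between the two contrasts remains (1.4 versus 6.5).

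Third, the contrast does not create benefit from an inert drug. If all four categories are distributed alike in both arms, its odds ratio is 1. This also stands: the fault is that a real effect on worsening is attributed to improvement or protection.

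Fourth, the damage is contained. The primary contrast keeps all evaluable ears. Worse versus other is its complement, so nothing is lost by leaving it off the list. Improved versus other is correctly specified. The outcome affected is a single secondary contrast in a Phase II proof-of-principle study. These points limit the severity but do not supply the missing analysis.

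**Conclusion.** The concern holds. Read as written, the first total-ear contrast in SAP 8.2 selects ears by their Month 6 outcome, contradicts Protocol 3.2.2 and SAP 3.2, and leaves one protocol endpoint without a total-ear analysis.

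Under the plan's 40% and 8% worsening rates, with equal improved or protected shares, the odds ratio moves from 1.0 to 5.0. The size rests on assumed category splits; the classification gap does not. SAP 6.7 plans no multiplicity adjustment for secondary outcomes, so nothing there would temper a misleading result. The text should be corrected before analysis, but the primary conclusion is not at risk.

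**What to change.** In SAP 8.2, change the first total-ear secondary contrast so that its comparator is worsened ears plus ears abnormal to the same degree at both visits, matching the best-ear contrast in that section. Add that all evaluable ears are included. Check that Table 21d, which reports treatment effects on total ears for each outcome, is programmed to this definition.

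The cost is one line of SAP text. No new data are needed, and the sample size and primary analysis do not change.

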#### **5.4.6. Handling of Withdrawals**

Study subjects may withdraw voluntarily from participation in the study at any time. Up to 20% (n=10) over-enrollment is allowed to replace subjects who drop-out or who have inadequate audiology assessments. Study subjects also may withdraw voluntarily from receiving the study intervention for any reason. If a study subject withdraws or is discontinued from the study at any time prior to completion of the study, the reason for this decision will be recorded on the electronic case report form (eCRF). SAEs and AEs will be followed according to guidelines in Section 9. The study subject should be encouraged to complete follow-up visits as part of the intent to treat group.

Should a study subject's therapy be discontinued prematurely, all clinical and laboratory evaluations scheduled during the next study visit will be completed on the day the study subject is discontinued. All randomized study subjects will continue to be followed as long as possible and included in the final analysis.

Since the primary endpoint requires comparison of baseline and 6 month audiology assessments, dropouts and subjects with audiology assessments that are inadequate for study comparison (Section 11.4.1) will be replaced. Characteristics of the dropouts and those with missing outcomes will be compared to determine if there is a difference between the two treatment groups. If differences are observed, this will be included in the primary outcome reporting as a limitation.

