### **6.3.1. Neutropenia**

If the ANC reproducibly (within one week) decreases to  $\leq 500$  cells/mm^3, study drug will be held until the ANC recovers to  $> 750$  cells/mm^3, and then administration of the drug will resume at the normal dose. If the ANC again reproducibly (within one week) decreases to  $\leq 750$  cells/mm^3, the study drug dosage will be reduced by 50% and maintained there as long as the ANC remains  $> 500$  cells/mm^3. If the ANC reproducibly (within one week) decreases to  $\leq 500$  cells/mm^3 on the 50% dosage, then the study medication will be discontinued. In cases of drug interruption, treatment will not be prolonged beyond the originally scheduled 6 week treatment timeframe.

Administration of granulocyte colony stimulating factor (GCSF) is allowed. All administered GCSF doses will be recorded on the concomitant medication sheet. The decision to utilize GCSF is left to the medical discretion of the participating investigator. The parameters for dose adjustment stated above, based upon ANC, will remain in effect even if the patient is receiving GCSF.

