### **9.5.2. Reporting Interval**

Document all AEs and SAEs from Study Day 1 through four weeks following the last dose of study drug.

All AEs and SAEs will be followed until resolution, even if this extends beyond the study-reporting period. Resolution of an AE is defined as the return to pretreatment status or stabilization of the condition with the expectation that it will remain chronic.

At any time after completion of the study, if the investigator becomes aware of an SAE that is suspected to be related to study product, the investigator will report the event.

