4.1 General Study Design and Plan

[figure not shown]
(ICH E3;9)

The current study evaluates whether six weeks of antiviral therapy can stabilize hearing deterioration in older infants, toddlers, and young children who have developed CMV-associated hearing loss. This study is a Phase II, international, multi-center, double-blind, placebo-controlled evaluation of six weeks of valganciclovir treatment for children (up to 4 years of age) with virologically-confirmed congenital CMV infection and hearing loss.

Patients meeting inclusion/exclusion criteria will be offered enrollment into the trial. Randomization on the study occurs when the diagnosis of congenital CMV infection is confirmed, and the subject is then assigned to receive either 6 weeks of oral valganciclovir or 6 weeks of placebo. Study subjects will be stratified according to age at randomization (1 through 11 months, 12 through 23 months, 24 through 35 months, and ≥ 36 months) and CMV involvements (symptomatic and asymptomatic at birth) as a marker of disease severity. An independent Data and Safety Monitoring Board (DSMB) will oversee the conduct of the trial. During the course of their oversight, they may request to have access to unblinded data.

The target sample size is 54 subjects (27 in each arm). Up to 20% over-enrollment will be allowed to replace subjects who drop-out or who have inadequate audiology assessments. The primary endpoint will be change in total ear hearing assessments (improved + no change versus other) between baseline and 6 months. Secondary and tertiary endpoints will be assessments of other measures of hearing outcomes; detection of viruria, viremia, and CMV in saliva by PCR six weeks and six months after trial entry; the quantitative log reduction in viruria, viremia, and CMV viral load in saliva detected after six weeks of therapy; correlation of change in viral load with change in total ear and best ear hearing at six months; incidences of unanticipated medically attended visits and adverse events which lead to permanent discontinuation of valganciclovir therapy or have an unresolved outcome; and assessments of blood concentration of ganciclovir after administration of valganciclovir. Stopping rules will be employed in order to limit exposure of study subjects to a potentially unacceptable treatment.

Figure 1: Schematic of Study Design

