- g) Valganciclovir or placebo administration begins on Day 1 of the study; study medication dose adjusted for weight change, if needed, at each study visit while on treatment

Hearing assessments at each time point and at each ear as well as the change in the best ear comparing Month 6 with baseline will be provided by a single Independent Audiologist (IA) who will interpret the audiology reports of all patients at all protocol-specified visits requiring hearing assessments. The IA will enter the data directly to the eDES.

Section 3.3 describes the derived variables and the techniques and rules used to obtain the transformed data that will be used in the analyses

5 Sample Size

(ICH E3; 9.7.2. ICH E9; 3.5)

The planned enrollment is 54 subjects. Dropouts and subjects with audiology assessments that are inadequate for study comparison will be replaced (up to 20%, or n=10).

A sample size of 54 (27 in each arm) has 90% power to detect a worsening of hearing from 40% to 8.0% in the treatment group based on analyzing two correlated binary outcomes with correlation coefficient of 0.55 at 2.5% level of significance (using PASS 2008 program).

6 General Considerations

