9.2 Adverse Events

Analyses of AEs will be based on data from all subjects receiving at least one dose of study drug. As per protocol, safety data will be collected only through Study Day 70, i.e., four weeks after the last study dose.

AEs will be reported by treatment based on the relation to study drug, toxicity grade, and body system. When calculating the incidence of adverse events, or any sub-classification thereof by treatment, time period, severity, etc., each subject will only be counted once and any repetitions of adverse events will be ignored; the denominator will be the total number in each treatment group or overall sample size as appropriate.

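### AE counts are compared by Poisson regression with no stated overdispersion correction or time-at-risk offset; if events cluster within children, p-values are too small and intervals too narrow

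*SAP*

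**What the plan says.** The count comparison appears three times. SAP Section 9 (Safety Analyses) states that a "Poisson regression model will be used to compare the number of AEs experienced by subjects between two groups". Protocol 11.4.2 states that a "Poisson regression model will be used to compare the number of AEs/SAEs experienced by subjects between the two groups", and SAP 8.2 repeats that sentence. Nothing is added on dispersion, variance estimation, covariates or exposure.

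Elsewhere the plan does name a term for within-child dependence: GEE for the two ears (SAP 8.1), a random intercept for repeated laboratory values (SAP 9.5), and a random intercept for AE grade (Table 10b in the SAP list of tables).

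The AE window is described in two ways. Protocol 9.5.2 says: "Document all AEs and SAEs from Study Day 1 through four weeks following the last dose of study drug". SAP 9 and 9.2 say that "safety data will be collected only through Study Day 70, i.e., four weeks after the last study dose". SAP 9.3, on SAEs, goes back to counting from the last dose. The two agree only when dosing ends on Day 42.

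**The concern.** A Poisson model fitted as written takes its standard error from the assumption that variance equals mean. The plan describes conditions in which child-level counts could vary more than that. Ages run from 1 month to the fourth birthday, and children may have been symptomatic or asymptomatic at birth. Abnormal laboratory findings count as AEs (Protocol 9.2.1), and safety bloods are scheduled on five days (1, 14, 28, 42 and 70). The rule in SAP 9.2 that ignores repeat events governs incidence tables, so repeats still enter the count model. If some children contribute many events and others few, the arms will look different by chance more often than the nominal rate.

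A separate issue is exposure. Under the protocol's window, a child who stops drug early is observed for fewer days. If that happens more in one arm, that arm accrues fewer counted events and looks safer than it is.

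**Working it through.** The documents give no AE rate, dispersion, rate ratio or power for this comparison, so there is no figure of the plan's to reproduce.

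**Inputs from the documents.** Arm size: "A sample size of 54 (27 in each arm) has 90% power" (SAP Section 5). Dropout allowance, used as the upper end for short follow-up: "Up to 20% over-enrollment will be allowed to replace subjects who drop-out" (SAP 4.1).

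**Assumptions, not in the documents.** Mean of 1, 2 or 4 AEs per child; gamma-Poisson counts with variance = μ + kμ², k from 0 to 1, so that φ = variance/mean = 1 + kμ; two-sided 5% test (0.05 is stated only for the primary outcome); up to 20% of children with half the time at risk.

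**1. Overdispersion, equal time at risk.** The true type I error of an unscaled Poisson Wald test is 2 × [1 − Φ(1.96/√φ)], and correct intervals are √φ times wider on the log scale. For φ = 2: 1.96/1.414 = 1.386, giving 0.166. The simulated column uses 20,000 null trials per setting, 27 per arm.

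| φ | Closed form | Simulated | Intervals should be wider by |
|---|---|---|---|
| 1 | 5.0% | 4.6-5.0% | 1.00 |
| 1.5 | 11.0% | 10.5-11.1% | 1.22 |
| 2 | 16.6% | 15.9-16.4% | 1.41 |
| 3 | 25.8% | 25.3-25.4% | 1.73 |
| 5 | 38.1% | 37.4% | 2.24 |

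In the same simulated trials a Pearson-scaled test holds 4.5-5.2%, and a robust variance with an n/(n−1) factor and a t reference holds 4.5-5.9%. The closed form does not contain n, so enrolling replacements would not change the picture.

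**2. Variation between randomisation strata.** Age group (4) and status at birth (2) give 8 strata, and stratified allocation balances differences between them. Simulation settings: 54 children, equal-probability strata, blocks of 4 (assumed; no block size is given), mean 4, all extra variation between strata.

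- φ about 1.9: 15.4% without stratification, 6.3% with it.
- φ about 3.2: 26.7% and 8.2%.
- φ about 4.2: 33.9% and 9.6%.

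When child-level variation within strata is added, the stratified figure returns to about 20-30%.

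**3. Unequal time at risk, no overdispersion, no offset.** If a share s of children in each arm has half the time, the expected rate ratio under equal true rates is (1 − 0.5s₁)/(1 − 0.5s₀).

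- Balanced, 10% or 20% in both arms: ratio 1; type I error 5.3-6.8%.
- 20% against 5%: 0.90/0.975 = 0.92; type I error 7.4-10.3%.
- 20% against 0%: 0.90; type I error 8.5-12.9%.

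A log-time offset returns all of these to 4.6-5.0%. Half the time is a severe case: half of 70 days is 35, which means a last dose on Day 7 (7 + 28 = 35). A last dose on Day 14 leaves 42/70 = 0.6 of the window, and 20% against 0% then gives 1 − 0.2 × 0.4 = 0.92. A last dose on Day 28 leaves 56/70 = 0.8, giving 0.96.

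**4. Both together** (μ = 2, k = 0.5, 20% against 5% with half time): no correction 18.2%; offset only 15.9%; scale and offset 5.1%. The two repairs address different faults.

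**The case against.** The strongest reply is that nothing in the documents shows overdispersion. At φ = 1 the planned test is valid, and the high error rates come from assumed inputs. Two obvious sources of heterogeneity, age and status at birth, are stratification factors, so stratified allocation removes most of the inflation they would cause. Repeated laboratory AEs are not established either: AEs are followed to resolution, and baseline conditions count only if they worsen, so a persisting abnormality may be a single event. The count model also drives no stated decision. Fisher's exact test on children with at least one AE is planned and is unaffected by clustering. The halting rule is per child, and no entry in the SAP list of tables carries a Poisson test.

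Most of this stands, and it sets the size and priority of the point. It does not remove it, because child-level variation within strata still inflates the error, and Fisher's test answers a different question from a comparison of event numbers.

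A reader might also infer that differing time at risk is itself what makes the intervals too narrow. The calculations do not support that: balanced differences move the error rate by less than 2 points, and the main effect of unbalanced ones is bias. The design also limits the spread. Drug can be stopped for toxicity (for neutropenia, after a further fall "on the 50% dosage, then the study medication will be discontinued"), but Protocol 5.4.6 says: "All randomized study subjects will continue to be followed as long as possible and included in the final analysis". That keeps children under observation, although Protocol 9.5.2 still closes AE recording four weeks after the last dose.

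**Conclusion.** The point holds as a gap in specification with a conditional consequence. Followed as written, the model understates uncertainty in AE counts whenever variance exceeds mean: type I error is about 11%, 16-17% and 25% at ratios of 1.5, 2 and 3 with child-level variation, less where the variation is between strata, and 5% with none. These figures rest on gamma-Poisson counts and on ratios that the documents neither give nor exclude.

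The exposure issue is a second, smaller fault: a possible bias in the rate ratio, confined to early stoppers and dropouts, and about 0.90 in a severe assumed case.

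Two stronger readings are not supported. The documents do not show that the AE p-values will be wrong. Nor do they prescribe an uncorrected model; they are silent, although they name a within-child term for other outcomes. The trial's safety assessment as a whole does not depend on this test. Priority is modest.

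**What to change.** In Protocol 11.4.2, SAP 8.2 and SAP 9, specify Poisson regression with a Pearson-estimated dispersion and a t reference, with log days at risk as offset. Negative binomial regression or a small-sample robust variance would also serve; of these, the Pearson-scaled and robust versions were the ones simulated here.

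Define days at risk as Day 1 to the end of the AE window or last contact, whichever comes first. Choose one window by reconciling four weeks after the last dose (Protocol 9.5.2, SAP 9.3) with Study Day 70 (SAP 9 and 9.2), and say how a child who stops drug early is counted. The offset assumes a roughly constant event rate over the window, which should be stated.

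The cost is one sentence in each place, no new data, and somewhat wider intervals if counts are overdispersed. If much of the variation turns out to lie between strata, a scaled model without the stratification factors will err on the conservative side; adding age group and status at birth as covariates, data permitting, would limit that. If there is no overdispersion, little is lost.
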